### ***Biostatistical Analysis***

#### **Sample Size:**

We estimated study size based on postoperative pain scores in a recent study of surgical patients at our institution (manuscript submitted); mean NRS was  $50 \pm 28$ . Our estimate for effect size is based on published data showing that a difference in NRS of 20/100 points is clinically significant. A sample size of 32 per group will have 80% power to detect a difference in means of 20 (the difference between a Group 1 mean,  $m_1$ , of 50 and a Group 2 mean,  $m_2$ , of 30) assuming the common standard deviation is 28 using a two group t-test with a 0.05 significance level. To account for dropout, we will enroll an additional 8 patients for each group for a total sample size of 80 patients.

Statistical Analysis:

Data will be summarized using descriptive statistics and will be presented as means (SD), medians [IQR] or frequency counts (%), as appropriate. Data will be analyzed on an intention to treat basis. We will first examine the success of randomization by comparing covariates demographic and clinical covariate measurements between the FULL-BUP and STD-BUP groups; to conserve study power, no formal statistical comparison will be performed and the data will be reviewed visually. Next we will perform univariate analyses to compare outcome measures between the FULL-BUP and STD-BUP groups, using a two-sided t-test or Mann Whitney U test for continuous variables and chi square or Fisher exact tests for categorical data, as appropriate. For paired analysis of pre/post surgery instruments, we will use McNemar's test or the Wilcoxon test, as appropriate. We will then explore the relationships between demographic and clinical variables and outcome measures in bivariate analyses, using the above methods or Pearson's and/or Spearman's correlation, ANOVA or Kruskal-Wallis test, as appropriate. Finally, we will explore further any observed differences in outcome measures between study arms by adjusting for covariates using analysis of covariance or (in the event of missing data), mixed models regression. Covariates will be entered into the model if they demonstrate a significant ( $p \leq 0.1$ ) association with outcome measures in bivariate analyses.

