We will perform an interim analysis at 50% enrollment and will terminate the study if a significant pain score difference is detected. Significance for the interim analysis will be accepted at  $p < 0.003$ , based on 2 sequential tests and using an O'Brien-Fleming spending function to determine test boundaries. Significance overall will be accepted at  $p < 0.047$  to account for interim analysis. All statistical analyses will be performed by the Navigation team at CORE using SPSS Statistical Software version 27 (IBM SPSS Inc., Armonk, NY).

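### The final threshold of p<0.047 is not the O'Brien-Fleming spending boundary that goes with an interim p<0.003; that boundary is p<0.049, and the stated pair is valid but slightly conservative

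*Combined protocol and SAP*

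**What the plan says.** All the relevant text is in the Biostatistical Analysis section of the combined protocol and SAP.

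- **Timing:** "We will perform an interim analysis at 50% enrollment". The study stops if the pain score difference is significant at that look.
- **Interim threshold:** "Significance for the interim analysis will be accepted at $p < 0.003".
- **Method:** "based on 2 sequential tests and using an O'Brien-Fleming spending function to determine test boundaries".
- **Final threshold:** "Significance overall will be accepted at $p < 0.047$ to account for interim analysis".
- **Sample size:** "A sample size of 32 per group will have 80% power to detect a difference in means of 20", with a common SD of 28, "using a two group t-test with a 0.05 significance level".
- **Dropout allowance:** "we will enroll an additional 8 patients for each group for a total sample size of 80 patients".
- **Sidedness:** outcomes are compared "using a two-sided t-test or Mann Whitney U test for continuous variables".

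**The concern.** The plan names a method, the number of tests, the timing of the interim, the overall level and the sidedness. Together these fix both thresholds, so the stated numbers can be checked. The interim value agrees with the method and the final value does not. The documents do not say how 0.047 was obtained.

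This is the decision rule for the primary outcome. As written, the number and the named method disagree for a final p between 0.047 and 0.049. Two analysts following the same text could reach opposite conclusions there, which is what pre-specification is meant to prevent. The plan also does not say whether the fixed numbers or the function governs if the information fraction at the interim is not exactly one half.

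**Working it through.** **Inputs from the plan.** Overall two-sided alpha 0.05; two looks; interim at information fraction t = 0.5; O'Brien-Fleming spending function; stated thresholds 0.003 and 0.047; 32 evaluable patients per group; difference 20; SD 28.

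**Step 1: interim boundary.** With 0.025 spent per side, the cumulative two-sided alpha spent at fraction t is

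α(t) = 4 × [1 − Φ(z / √t)], where z = Φ⁻¹(1 − 0.05/4) = 2.2414.

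At t = 0.5, z/√t = 2.2414/0.7071 = 3.170, so α(0.5) = 0.00305. The interim critical value is z₁ = 2.963. The plan's 0.003 is reproduced.

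**Step 2: final boundary.** The two test statistics are bivariate normal with correlation √t. The final critical value z₂ solves

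1 − P(|Z₁| < 2.963, |Z₂| < z₂) = 0.05, with correlation √0.5.

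Numerical integration gives z₂ = 1.9686, a nominal two-sided p of 0.0490. The plan's 0.047 is not reproduced.

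**Step 3: does another version of the method or another information fraction give the pair?**

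| Version | Interim p | Final p |
|---|---|---|
| Stated in the plan | 0.003 | 0.047 |
| Spending function, 0.025 per side, t = 0.45 | 0.0017 | 0.0494 |
| same, t = 0.50 | 0.0031 | 0.0490 |
| same, t = 0.55 | 0.0050 | 0.0484 |
| same, t = 0.60 | 0.0076 | 0.0476 |
| same, t = 0.65 | 0.0109 | 0.0466 |
| Form spending the two-sided 0.05 directly, t = 0.50 | 0.0056 | 0.0478 |
| Classic O'Brien-Fleming, t = 0.50 | 0.0052 | 0.0480 |

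Under the per-side spending function that reproduces the plan's interim value:

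- The interim value rounds to 0.003 only for t between 48.2% and 51.3%, where the final value is 0.0489 to 0.0492.
- The final value rounds to 0.047 only for t between 60.5% and 65.6%, where the interim value is 0.0079 to 0.0113.

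The two ranges do not overlap, so rounding is not the explanation. At t = 0.5, a final level of 0.047 that used the full 0.05 would go with an interim level of 0.0070.

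**Step 4: type I error.** Overall alpha = 1 − P(|Z₁| < z₁, |Z₂| < z₂).

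| Fixed pair | t = 0.40 | t = 0.50 | t = 0.625 |
|---|---|---|---|
| 0.003 / 0.047 | 0.0484 | 0.0480 | 0.0475 |
| 0.003 / 0.049 | 0.0504 | 0.0500 | 0.0495 |

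**Step 5: power at 32 per group.** The noncentrality parameter is (20/28) × √(32/2) = 2.857 with 62 degrees of freedom. Two-sided t-test power for a single final test is 80.3% at 0.05 (the plan's 80% is reproduced), 80.1% at 0.049 and 79.5% at 0.047. With both looks simulated (3,000,000 trials, 16 per group at the interim), power is 79.6% for 0.003/0.047 and 80.1% for 0.003/0.049.

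**The case against.** The strongest reply is that 0.047 has an obvious source. The named function spends 0.00305 at the interim, and 0.05 − 0.00305 = 0.04695, which rounds to 0.047. Using the unspent alpha as the final threshold is a valid Bonferroni-type split, fixed in advance, that keeps the overall error below 0.05. The method is also named in the sentence about the interim, and the final level is given in a separate sentence that does not repeat it. On that view the plan needs at most a clarifying clause.

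Part of this stands. The origin is plausible, though the documents do not state it, and the rule does control type I error. But unspent alpha is not a spending-function boundary: it ignores the correlation between the looks, which is what raises the final level to 0.0490. The text also speaks of boundaries in the plural, for two tests, so the natural reading is that both come from the function.

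A second reply concerns the information fraction. If all 40 patients at the interim were evaluable against 64 at the end, t would be 40/64 = 62.5% and the function would give 0.0092 and 0.0471. That would require 16 losses, all among the last 40 patients, which is implausible. Equal dropout in both halves (32/64) or none (40/80) gives 50%, and a 24-hour primary outcome leaves little follow-up lag. This is fair. The case shows only that the thresholds move with the fraction; the mismatch at 50% does not depend on it.

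**Conclusion.** The concern holds. Under the method the plan names, with a two-sided 0.05 and the interim at 50% information, the final threshold is p<0.049, not p<0.047. The stated pair is valid and conservative, with an overall alpha of 0.0480 against the 0.05 allowed. The cost is about half a percentage point of power, which still rounds to 80%, and a different verdict only for a final p between 0.047 and 0.049. No false-positive claim is put at risk and the sample size does not need to change. The point is worth correcting because the primary decision rule should agree with its named method, not because the numerical effect is large.

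The result rests on the usual large-sample joint normal distribution of the two test statistics and on information being proportional to the number of evaluable patients.

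**What to change.** Either of two changes resolves it.

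1. State the final boundary as p<0.049, and add that both boundaries will be recomputed from the O'Brien-Fleming spending function at the information fraction (evaluable patients) actually observed at the interim. The second part is needed: fixed at 0.003/0.049, the overall alpha would be 0.0504 if the interim fell at 40% information.
2. Keep 0.047, describe it as a deliberately conservative choice and not as the O'Brien-Fleming boundary, and give the power at that level (about 79.5%).

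The first is preferable because number and method then agree and the small loss of power is recovered. The cost is one number and one sentence in the statistical text, with no change to sample size or conduct. It should be done before the interim analysis, since changing a significance threshold after data have been seen would be hard to defend.

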### ***Limitations***

[figure not shown]
A study limitation is that pain scores, craving scales, and drug use are all self-reported measures, therefore complete accuracy cannot be assured. However, our randomization design should help prevent the introduction of bias, as inaccuracies based on self-report subjectivity would be randomly distributed between the two treatment arms. To encourage accurate drug-use reporting, we will remind participants that information they provide regarding drug use will not be included in their patient record, nor will their providers have access to the information. Another limitation is that our study does not have a placebo arm, however, since randomization occurs prior to hospital admission and physical interaction with study staff, it is impractical to provide patients with placebo medication at the time of study commencement. An additional limitation is that the study is not blinded to patients or treatment providers, however, we attempt to mitigate this limitation by masking the data collection and data entry, as described in the study design and research procedures section.

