### ***Data Integrity and Privacy Protection***

Our study will use a data safety monitoring board (DMSB) that will be scheduled to meet once the study reaches 50% enrollment and in response to any adverse event. The DSMB will review the progress of the study, monitor data, identify any inconsistencies or errors in data collection, and review patient safety. Any errors in data collection that are identified will be reconciled immediately to ensure the validity of our findings. The DSMB will also ensure that this study will not continue to enroll patients if one treatment modality shows early and significant superiority. Below is a table of major and minor adverse outcomes (AEs) that will be reported to the DSMB during the study period and the actions that will be taken. Any unanticipated adverse events will be reported within 7 days. For patients who experience AEs related to substance use in the outpatient setting, [name] will provide patients with information regarding community resources available to patients- such as support groups and harm reduction resources. Study staff will contact the patient's buprenorphine provider on record, as well.

Table 1: Major and Minor Adverse Events

|          | Item  | Action   | Regulatory Reporting   |
|----------|---|--|--|
| Major AE | 1. ED admission due to severe pain
2. Intractable Pain   | Alert acute pain service (APMS) for management recommendations   | Immediate to DSMB; Within 7 days to IRB                            |
|          | 3. Opioid misuse/relapse
4. Opioid overdose
5. Opioid Withdrawal                                | Alert buprenorphine provider on record immediately; provide patients with community resources to seek help as needed |  |
| Minor AE | 1. Hospital discharge delay due to poor pain control
2. Pain worse than anticipated
3. Cravings | Alert integrated medication assistance treatment (iMAT) team and APMS as needed                                      | Within 30 days of event to DSMB; DSMB reports to IRB within 7 days |

The DSMB will determine study stop rules; however, we will recommend to them that when 10 patients have been enrolled in each group (25% enrollment), if >7 in either group have intractable pain interfering with hospital discharge or opioid overdose within 2 weeks of discharge, the study should be terminated. The DSMB members are [name] (Dept. of Anesthesiology); [name] (Dept. of Anesthesiology); [name], NP (Psychiatric Nurse

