Practitioner); [name] (Inpatient Psychiatry Consultation-Liaison Team) ; [name] (Senior Biostatistician, MMCRI/CORE); and [name] (Family Medicine, Maine Medical Partners, graduate of MMC Addiction Medicine Fellowship). [name] (Faculty Scientist, Critical Care Pharmacy) will be the medical monitor for this study.

All phases of this study will comply with Health Insurance Portability and Accountability Act (HIPAA) regulations. Data will be collected and stored in a REDCap database to preserve privacy and confidentiality. The 30-Day Timeline Followback will be completed on Timeline, a website (<https://www.smashlabs.org/timeline>) developed and supported by Brown University. Please also refer to the PDF copies of this data collection tool included in the IRBNet package. The responses on the Timeline website will be identified by study numbers only, no PHI will be collected or stored on this site. Information regarding substance abuse history, including illicit narcotic use, will remain confidential and personal identifiers will be removed during data storage. Only members of the research team will have access to the data that participants have consented to provide. Participants will be informed that they have the right to not answer any question that makes them feel uncomfortable.

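### Participants are told that providers will not learn of their self-reported drug use, yet Table 1 requires an immediate alert to the buprenorphine provider for misuse or relapse

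*Combined protocol and SAP*

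**What the plan says.** The Limitations section acknowledges that "pain scores, craving scales, and drug use are all self-reported measures". To improve the accuracy of drug-use reports, staff are to give participants this reminder: "information they provide regarding drug use will not be included in their patient record, nor will their providers have access to the information".

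The Data Integrity and Privacy Protection section adds a general access rule: "Only members of the research team will have access to the data that participants have consented to provide". It also says of the online calendar instrument that "The responses on the Timeline website will be identified by study numbers only".

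The same section sets the safety duty. Table 1 lists "Opioid misuse/relapse" as a major adverse event, with the action "Alert buprenorphine provider on record immediately". The text before the table repeats the duty. It begins "For patients who experience AEs related to substance use in the outpatient setting" and goes on to say that study staff will contact the "buprenorphine provider on record, as well".

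**The concern.** The reminder and the alert concern the same information and the same recipient. The buprenorphine provider is one of the participant's providers; the Randomization Plan and Safety sections both describe that clinician as the participant's own. If a participant tells staff of a relapse, alerting the provider passes on what the participant was told the provider would not have.

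This is a matter of participant protection in people with opioid use disorder. In the self-report case there are two possible outcomes, and staff have no written rule for choosing between them:

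- A disclosure made under an unqualified assurance is passed to the clinician who prescribes that person's treatment.
- A major adverse event does not receive its required immediate action.

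The conflict also bears on the secondary self-reported drug-use measures (the Current Opioid Misuse Measure, COMM, and Timeline Follow-Back), whose candour the reminder is meant to support.

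**Working it through.** The point is textual, so there is no plan figure to reproduce and no rate or effect to compute. The check sets the statements side by side and looks for anything that reconciles them.

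**1. The assurance.** The reminder in Limitations covers the information participants give about drug use, and it excludes both the patient record and the providers. It carries no exception. The access rule in Data Integrity and Privacy Protection limits access to the research team, also without exception.

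**2. The duty.** Table 1 and the text before it require contact with the buprenorphine provider. Neither limits the duty by how the event came to light, and neither requires the participant's agreement.

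**3. Scope within Table 1.** Of the five major events, items 1 and 2 go to the acute pain service. Items 3 to 5 carry the provider alert, so 5 − 2 = 3 of 5. The finding is claimed for one of those three, item 3 (misuse or relapse).

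**4. Does each route to the event create a conflict?**

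| How staff learn of misuse or relapse | Conflict? |
|---|---|
| From the buprenorphine provider | No; the provider already knows |
| From MainePAT or the medical record | No; it is not information the participant supplied |
| From the participant after surgery | Yes; the alert conveys what the participant disclosed |

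**5. Is the third route part of the plan?** Limitations describes drug use as self-reported. Study Procedures schedules a substance use evaluation one month after surgery, repeating the self-assessments from the day of surgery. Measures for Aim 3 uses COMM to detect misuse, which is also the event named in Table 1. The other planned sources are narrower: Measures for Aim 4 describes MainePAT as tracking prescribed medications, and Study Procedures describes the provider contact as collecting treatment retention.

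**6. Boundaries.** Baseline reports of use before surgery are not counted. The plan does not say that COMM or Timeline Follow-Back answers are screened for Table 1 events, and Timeline answers carry study numbers only. Whether a questionnaire answer alone triggers the alert is therefore open. The clear case is direct postoperative disclosure to staff.

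**7. Result.** In that case, carrying out the Table 1 action gives the provider the information that the reminder says the provider will not have. Keeping the reminder's promise means omitting the action.

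**The case against.** The strongest objection is that the two texts deal with different things. The reminder follows a remark about self-reported measures and aims at accurate reporting, so it may refer only to research answers. The access rule likewise speaks of data. The alert concerns adverse events and their clinical management. The access rule and the alert sit in the same section, which suggests the authors kept event notification and dataset access apart. This does not remove the conflict. The reminder is worded to cover the information itself, and an alert about a self-disclosed relapse conveys that information whether or not the provider ever sees a questionnaire.

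A second objection is that no procedure links questionnaire answers to Table 1, and that the described staff calls collect pain scores and pain medication use or give reminders. This stands as a limit: self-report is a planned outcome measure but is not documented as the route for finding adverse events. The conflict is shown for disclosure to staff and left open for questionnaire answers.

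A third is that the consent form, which would normally set out the limits of confidentiality, was not available, nor was part of the protocol just before Limitations. This also stands. An exception there would reduce the matter to aligning wording, though the reminder as written would still omit it.

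Finally, the conflict could be resolved the other way, by limiting the alert to events learned outside the confidential questionnaires or to cases where the participant agrees. That is a legitimate alternative for the ethics committee to weigh, but it weakens a safety action.

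**Conclusion.** The concern holds. When study staff learn of postoperative misuse or relapse from the participant, the reminder and the Table 1 alert cannot both be followed, and no exception appears in the available text. It should be fixed, as a matter of participant protection.

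Its size is limited. How often the situation would arise cannot be estimated from the documents. The finding does not bear on the primary pain outcome, the sample size or the interim rule, and no difference between arms is claimed. Confidence is medium, because the conclusion assumes that neither the consent text nor the unavailable part of the protocol already states the exception.

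**What to change.** Check the consent text first. If it already states an exception, align the reminder, the access rule and the adverse-event text with it. If it does not, add the exception there as well.

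Keep the Table 1 duty. Qualify the reminder in Limitations and the access rule in Data Integrity and Privacy Protection, for example: *Your answers about drug use will not be placed in your medical record or shared with your providers, with one exception: if study staff learn of an event for which the study's safety plan requires an alert, they will tell your buprenorphine provider.* Because the wording refers to any event that carries the alert, it also covers overdose and withdrawal.

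The cost is one sentence in the reminder, matching protocol wording and an IRB amendment. Some participants may be less candid on COMM and Timeline Follow-Back once the exception is stated. That loss falls on secondary measures and is a reasonable price for an assurance that staff can keep.

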### ***Study Timeline and Future Plan***

We anticipate it will take 11 months to complete the subject recruitment for this trial. Data collection will begin at month 2 of the funding period and will be completed by month 12. Data analysis will begin at month 6 of the funding period and will be completed by month 12.

The findings obtained from this study will provide the framework for investigating strategies to improve postoperative treatment retention and relapse. The perioperative period can be highly stressful and providing patients with analgesic medications abused in the past can be a strong trigger for relapse. We anticipate our research findings will help us identify the major points to focus on in future investigations identifying ways to reduce postoperative OUD symptom severity.

